11.5 Secondary Efficacy Analysis: NEWS

11.5.1 Time to the earlier of discharge or NEWS of ≤ 2 maintained for 24 hours

The time to earlier of discharge or NEWS of ≤ 2 maintained for 24 hours (Days) is defined as:

Date of First earlier of discharge or NEWS of ≤ 2 maintained for 24 hours – Date of Baseline Assessment + 1.

If the patient did not experience discharge or NEWS of ≤ 2 maintained for 24 hours, the patient will be censored at the last known date the patient is known to not have experienced either of these events:

Final Date of Confirmation of no discharge nor NEWS of ≤ 2 maintained for 24 hours - Date of Baseline Assessment + 1.

If a patient died before discharge or NEWS of ≤ 2 maintained for 24 hours, the patient will be censored as a competing risk based on the following:

Date of Death - Date of Baseline Assessment + 1.

11.5.2 NEWS by timepoint

Descriptive statistics treating NEWS scale as continuous data in accordance to [section 3.1](#) will be reported for each treatment arm and overall at Baseline, Day 3, 5, 8, 11, 15 and 29. Change from baseline descriptive statistics will also be given for these timepoints for each treatment arm and overall. P-values and 95% CI comparing the differences between SOC and treatment arms A and B will also be provided for change from baseline analysis using a mixed model with treatment arm, age, day, site, interaction between day and treatment arm as fixed effects and patients as random effects with random intercepts.

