2. PROJECT OVERVIEW

2.1 Study Design

This is a Phase 2b/3, multicenter, open label, randomized, parallel group study to evaluate the efficacy of Ifenprodil in patients with coronavirus disease of 2019 (COVID-19) disease.

In the Phase 2b phase, patients will be randomized in a ratio of 1:1:1 to either a) 20 mg TID IP plus Standard of Care group, b) 40 mg TID IP plus Standard of Care or c) Standard of Care only group. Investigators will collectively enroll approximately 50 evaluable patients in each treatment group, for a total of 150 patients. Patients receive either oral Ifenprodil (20 or 40 mg ter in die (TID)) for up to 14 days in addition to Standard of Care, or Standard of Care only. The Standard of Care (SOC) for each patient will be captured in the electronic clinical reporting form (eCRF).

Randomization will be stratified by site, and age (<65 versus ≥65).

For Phase 2b, one interim statistical analysis will be performed on selected efficacy endpoints and for safety for each arm after the first 75 patients have completed up to 2 weeks of treatment (Day 15). This analysis is being done to allow safety assessment and some snapshots of efficacy assessments as the trial progresses.

The Phase 2b study will also evaluate the different constructs of the ordinal scale (different days and different number of categories) by severity (severe vs. mild-moderate). Data from the Phase 2b study will be used to down select and prioritize the secondary endpoints. The protocol would then be amended for Phase 3 study to include the additional required number of patients to be recruited for the study to meet statistical significance in its primary endpoint.

An additional placebo arm will be added in the Phase 3 portion of the study. The number of participants to be enrolled in Phase 3 pivotal stage will be determined based upon the outcome of pilot Phase 2b stage of the study. Participants will be randomized to receive investigational product (IP) plus SOC, or Placebo plus SOC. Details will be outlined in a protocol amendment

Figure 1: Trial Design

[figure not shown]

Table 1 Schedule of Events

Trial Activity	Screening/Baseline/ Enrolment visit	Daily until hospital discharge	End of treatment	Follow-up period	
Day	1	2-14	15	29	60
Allowed window for visit (±)	-1 ^a		2	2	3
Visit	1		2 ^b	3	4
Informed consent	•				
Inclusion/exclusion criteria including confirmation of COVID-19 diagnosis	•				
Confirmation SARS-CoV- 2 ^h	•	•	•	•	
Pregnancy test	•				

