Demographics/Medical History	•				
Physical Exam	•				
Vital signs ^c	•	•	•	•	
Clinical support data collection ^f	•	•	•	•	
Safety Laboratory Testing ^d	•	•	•	•	
Cytokine Markers ^k	•	•	•		
Child-Pugh Score ⁱ	•	•			
PaO2 and PaO2/FiO2 ratio ^j	•	•	•	•	
ECG	•				
Cough Severity (VAS) ^e	•	•	•	•	
Extent of Dyspnea (Likert Scale) ^e	•	•	•	•	
Adverse Events documented	•	•	•	•	•
Concomitant Medications	•	•	•	•	
Randomization	•				
Administer IP	•	•			
Vital Status					• ^g

^a Screening/baseline may occur up to 24 hours prior to randomization

^b Treatment can be given up to 14 days post randomization, or until hospital discharge, whichever comes first. If patient is discharged prior to Day 14, the next visit should be Visit 2.

^c Includes blood pressure (measured after the patient has been in a seated position (if possible) for ≥3 minutes of rest), pulse, respiratory rate, body temperature, and SpO2. Body weight and height will be measured at the screening visit only.

^d Baseline, Days 3, 5, 8, 11 if hospitalized, Day 15, Day 29

^e Baseline, Days 2, 4, 8, and 14 if hospitalized, Day 15 (if not done Day 14), Day 29

^f Includes NEW Score, on Baseline, Days 3, 5, 8, 11 if hospitalized, Day 15, Day 29

^g Vital status (is patient alive)

^h Baseline, Days 5 (or discharge, whichever comes first) and 15. Day 29 for patients with viral RNA detected at Day 15. Qualitative (mandatory) and Quantitative (if available) testing done all days.

ⁱ Baseline, Days 3, 5, 8, 11 if hospitalized

^j Minimum complete baseline, Days 3, 5, 8, 11, 15 and 29. If PaO2 not able to be taken, SpO2 should be obtained using a forehead sensor. Fingertip probes may be used if forehead sensors are not available. Remain consistent with the method of testing for the patient over the course of the study.

^k Cytokine markers at Baseline, Day 5, Day 15 (if available per local lab): IFN- γ , GM-CSF, IL-6, IL-12, TNF- α

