2.2.2 Secondary objectives

To investigate the clinical efficacy of NP-120 (20 and 40 mg TID) as compared to the control arm as assessed by:

- **Ordinal scale:**
 - Time to an improvement of one category from baseline on an ordinal scale.
 - Patient clinical status on an ordinal scale at days 3, 5, 8, 11, and 29.
 - Mean change in the ranking on an ordinal scale from baseline to days 3, 5, 8, 11, 15 and 29 from baseline
- **National Early Warning Score (NEWS)**
 - The time to discharge or to a NEWS of ≤ 2 and maintained for 24 hours, whichever occurs first.
 - Change from baseline to days 3, 5, 8, 11, 15, and 29 in NEWS
- **Oxygenation:**
 - Oxygenation free days in the first 28 days (to day 29)
 - Effect on the rate of change of partial pressure of oxygen (PaO₂) and PaO₂/FiO₂ ratio taken at baseline and measured once daily up to 2 weeks of treatment in IP versus control group patients
- **Mechanical Ventilation:**
 - Ventilator free days in the first 28 days (to day 29)
 - Incidence and duration of new mechanical ventilation use during the trial
- **Hospitalization:**
 - Duration of hospitalization (days)
 - Time to discharge (days)
- **Mortality:**
 - 15-day mortality
 - 28-day mortality

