3.2 General Key Definitions

The following definitions will be used:

- Date of the First Study Treatment Administration: The date of the first study treatment administration is defined as the earliest date on which a study treatment was administered.
- Date of the Last Study Treatment Administration: The date of the last study treatment administration is defined as the latest known date on which a study treatment was administered.
- Baseline: The Baseline value is value taken on Day 1. If Day 1 value is missing, Baseline is defined as the last available valid, non-missing observation for each patient prior to first study treatment administration on Day 1. Repeat and unscheduled assessments will be included in the derivation of the Baseline values only if Baseline visit value is missing.
- Change from Baseline: The absolute change from Baseline value is defined as the difference between the result collected/derived at a post-baseline visit and the Baseline value.

The change from Baseline value at each post-baseline visit will be calculated for all continuous parameters using the following formula:

$$\text{Change from Baseline Value} = \text{Result at post-baseline visit} - \text{Baseline Value}$$

The change from Baseline value will only be calculated if the specific post-baseline visit result and the Baseline value for the parameter are both available and will be treated as missing otherwise. In the data listings, the change values will be set to '-' (not applicable) for pre-baseline assessments.

The rate of change from baseline is defined as: Change from Baseline value/Baseline Value

- Study Day: The study day of an event is defined as the relative day of the event starting with the date of the first study treatment administration (reference date) as Day 1 (there will be no Day 0).

The study day of events occurring before the first study treatment administration will be calculated as:

$$\text{Study Day} = (\text{Date of Event} - \text{Date of First Study Treatment Administration})$$

For events occurring on or after Day 1, study day will be calculated as:

$$\text{Study Day} = (\text{Date of Event} - \text{Date of First Study Treatment Administration}) + 1$$

Study days will only be calculated for events with complete dates and will be undefined for events that are 'Ongoing' at the end of the study.

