11.4.2 WHO-7 Ordinal scale by timepoint

Descriptive statistics treating WHO-7 scale as continuous data in accordance to [section 3.1](#) will be reported for each treatment arm and overall at Baseline, Day 3, 5, 8, 11, 15 and 29. Change from baseline descriptive statistics will also be given for these timepoints for each treatment arm and overall. P-values and 95% CI comparing the differences between SOC and treatment arms A and B will also be provided for change from baseline analysis using a mixed model with baseline, treatment arm, age, day, site, interaction between day and treatment arm as fixed effects and patients as random effects with random intercepts using unstructured covariance structure. In the event of non-convergence, a simplified covariance structure may be chosen.

```
Proc Mixed data = adef;
class site trt subjid day;
model chg_bl = baseline site trt age day trt*day/ddfm=kr;
random int/sub= subjid type= un;
LSMEANS Trt*day / AT MEANS CL DIFF SLICE = day;
run;
```

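### The NEWS change-from-baseline model omits baseline NEWS, unlike the matching WHO-7 model, and gives up precision that would cost almost nothing to keep

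*SAP*

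**What the plan says.** SAP 11.5.2 (NEWS by timepoint) promises p-values and 95% confidence intervals for each ifenprodil arm against standard of care. They come from a "mixed model with treatment arm, age, day, site, interaction between day and treatment arm as fixed effects", with random intercepts for patients. No model code is given.

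SAP 11.4.2 (WHO-7 by timepoint) uses the same kind of analysis but specifies a "mixed model with baseline, treatment arm, age, day, site, interaction between day and treatment arm as fixed effects". Its SAS statement agrees with the prose: "model chg_bl = baseline site trt age day trt*day/ddfm=kr". Baseline enters there as a main effect only.

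The endpoint is a named secondary objective in SAP 2.2.2: "Change from baseline to days 3, 5, 8, 11, 15, and 29 in NEWS". Footnote f of the SAP schedule of events (Table 1) reads "Includes NEW Score, on Baseline, Days 3, 5, 8, 11 if hospitalized, Day 15, Day 29". SAP 3.2 adds: "The change from Baseline value will only be calculated if the specific post-baseline visit result and the Baseline value" are both present. Randomization is stratified by site and age group only (SAP 2.1 and 2.6). Protocol 10.9.2 gives no NEWS model that would supply the missing term.

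**The concern.** The two models match in every fixed effect except baseline, and the documents do not explain the difference. Baseline NEWS is not a stratification factor, so with about 50 patients per arm the arms can differ on it by chance. A change score that is not adjusted for baseline carries part of that difference into the treatment estimate. It is also, in general, noisier than the adjusted estimate.

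At stake is the precision of six planned NEWS comparisons per arm. SAP 2.1 says the Phase 2b data will be used to narrow down and rank the secondary endpoints. If WHO-7 is adjusted for its baseline and NEWS is not, the two are compared on unequal terms.

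**Working it through.** **Inputs from the documents.** The fixed effects are those in SAP 11.5.2 and 11.4.2. On size, SAP 2.1 says: "Investigators will collectively enroll approximately 50 evaluable patients in each treatment group, for a total of 150 patients". There is no planned SD, correlation or power for NEWS, so there is no figure to reproduce.

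**Assumed inputs.** s0 and s1 are the SDs of NEWS at baseline and at follow-up, and r is their correlation. All three are taken after age and site, which are already in the model. The formulas below are for one timepoint with complete data.

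**Variance of the arm difference** (up to a common factor):

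- Unadjusted change: s0² + s1² − 2·r·s0·s1
- Change adjusted for baseline: s1²(1 − r²)
- Difference: s0² − 2·r·s0·s1 + r²·s1² = (s0 − r·s1)², which is never negative

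Apart from the one degree of freedom used, adjustment at a single timepoint therefore cannot lose precision. The gain is zero only when s0 = r·s1.

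**Equal SDs.** The ratio is 2(1 − r)/(1 − r²) = 2/(1 + r). The next columns are √ratio, 50/ratio, and the power left if the adjusted analysis had 80% at two-sided 5%, which is Φ(2.802/√ratio − 1.960).

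| r | Variance ratio | SE ratio | Adjusted-analysis patients per arm that 50 unadjusted are worth | Power without baseline |
|---|---|---|---|---|
| 0.2 | 1.67 | 1.29 | 30.0 | 58% |
| 0.5 | 1.33 | 1.15 | 37.5 | 68% |
| 0.7 | 1.18 | 1.08 | 42.5 | 73% |
| 0.9 | 1.05 | 1.03 | 47.5 | 78% |

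**Unequal SDs.**

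- Baseline SD half the follow-up SD: the ratio is (1.25 − r)/(1 − r²). This gives 1.05/0.96 = 1.09 at r = 0.2, 0.75/0.75 = 1.00 at 0.5 and 0.55/0.51 = 1.08 at 0.7.
- Follow-up SD half the baseline SD: the ratio is (1.25 − r)/[0.25(1 − r²)], which is 4.0 at r = 0.5.

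**Chance imbalance.** The slope of change on baseline is r·s1/s0 − 1, which is −(1 − r) with equal SDs. That share of any baseline difference carries into the arm difference, in the opposite direction. With 50 per arm the baseline mean difference has standard error √(2/50) = 0.2 SD. At r = 0.5, an imbalance of that size moves the estimate by 0.1 SD.

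**Check with repeated visits.** A simulation used three arms of 50, six post-baseline visits, one common baseline slope, equal SDs, complete data and 4000 runs per setting.

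- Constant correlation: the Day 15 ratios were 1.34, 1.15 and 1.05 at r = 0.5, 0.7 and 0.9, close to the formula. The unadjusted estimate moved by −0.50 per unit of imbalance at r = 0.5, and by about zero after adjustment.
- Correlation decaying over time: the ratios were 1.37 to 1.87, for baseline-to-Day-15 correlations from 0.45 down to 0.05.

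**The case against.** The strongest reply is about size. No correlation or SD for NEWS is available, and a range of r that stops at 0.5 would flatter the gain: at r = 0.7 to 0.9 the variance excess is only 18% to 5%. Eligibility is limited to WHO-7 scores 4 and 5 (Protocol 5.1), so baseline NEWS could vary less than follow-up NEWS, and the gain could then almost vanish. This stands. The direction is secure, but the amount is not.

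The formula is also a complete-data result. NEWS on Days 3, 5, 8 and 11 is taken only in patients still in hospital, so 50 per arm will not hold at those visits. This stands too, although it does not favour leaving baseline out. If baseline severity predicts discharge, which is plausible but not stated, conditioning on baseline would make the model's missing-data assumption easier to defend.

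Finally, this is one unpowered secondary analysis in a stage that the SAP itself treats as exploratory (11.1), and no decision rule depends on its p-value. The omission may be a drafting slip, since 11.5.2 also lacks the code, covariance structure and non-convergence fallback given in 11.4.2. That bears on importance, not on whether to correct it.

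Two stronger readings are tempting. A reader might infer that the NEWS comparison is biased or invalid. The documents do not support that: arms are randomised, the unadjusted change contrast is unbiased on average with complete data, and its confidence interval already allows for chance imbalance. A reader might also infer that consistency with 11.4.2 requires a baseline-by-day term, but 11.4.2 has no such term.

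**Conclusion.** The point holds as a loss of efficiency. SAP 11.5.2 omits a covariate that its sister model includes, that is scheduled for collection, and that the outcome already requires.

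Under equal SDs, one timepoint and complete data, the variance is 1.05 to 1.67 times what it need be for r from 0.9 down to 0.2. The true figure could be close to 1.0 or well above this range, depending on the SD ratio. The never-below-1 result is exact for a single timepoint, apart from the one degree of freedom. With a common slope across visits it is supported by the simulated settings, not proved in general.

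This is a free improvement to a secondary analysis. It does not threaten the trial's main conclusions.

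**What to change.** In SAP 11.5.2, add baseline NEWS as a fixed covariate (main effect) and give the model statement in the form used in 11.4.2. Alternatively, state why the two models differ. The covariance structure and non-convergence fallback could be carried over from 11.4.2 at the same time.

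A baseline-by-day interaction is optional. It would help if the baseline correlation fades over the visits, because one common slope then leaves a little imbalance uncorrected: in the decaying-correlation simulations, up to about 0.13 per unit of imbalance at Day 15.

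The main effect costs one model term and one degree of freedom, with no new data and no patients lost. It should be settled before results by arm are examined, since Phase 2b is open label and a covariate added later would look chosen after the fact.

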11.6 Secondary Efficacy Analysis: Respiratory Support

For the part of the analysis, respiratory support is defined as:

- Any respiratory support (any of Oxygenation only, Mechanical Ventilation (Invasive and non invasive), ECMO)
- Oxygenation only
- Invasive Mechanical Ventilation
- Non Invasive Mechanical Ventilation
- ECMO

11.6.1 Rate of Respiratory Support: Oxygenation only, Mechanical Ventilation (Invasive and non invasive), ECMO

Counts and percentages of patients for respiratory support at least once will be reported for each treatment arm. If patients were eligible for respiratory support but did not receive one due to lack of resources, an additional analysis on counts and percentages of patients required to receive respiratory support will be reported for each treatment arm. Separate 95% CIs (Newcombe) and p-values (Chi-Squared test without continuity correction) will be computed between SOC and treatment arms A and B for patients with at least one respiratory support.

11.6.2 Duration of Respiratory Support: Oxygenation only, Mechanical Ventilation (Invasive and non invasive), ECMO

Counts and percentages of patients with the following categories (based on total number of hours of respiratory support) will be reported for each type of respiratory support and for each treatment arm. The duration calculation is only applicable to patient with respiratory support. For patients with ongoing respiratory support with no end date and time at data cut off, the date of data cut off will be used to calculate the end date for the ongoing at time of data cut off category.

The duration is defined as:

Date and time at end of respiratory support-Date and time at end of respiratory support.

- < 6 hours
- \geq 6 hours but < 12 hours
- \geq 12 hours but < 24 hours
- \geq 24 hours but < 72 hours
- \geq 72 hours but < 120 hours
- > 120 hours
- Ongoing at time of data cut off (\geq 6 hours) [The hour can be amended based on real data]
- Ongoing at time of data cut off (\geq 12 hours) [The hour can be amended based on real data]
- Ongoing at time of data cut off (\geq XX hours) etc...
- Prolonged respiratory support (consecutive respiratory support for 21 days with at least \geq 6 hours per day)

Separate 95% CIs (Newcombe) and p-values (Chi-Squared test without continuity correction) will be computed between SOC and treatment arms A and B for prolonged respiratory support.

11.6.3 Time to Respiratory Support: Oxygenation only, Mechanical Ventilation (Invasive and non invasive), ECMO

The time to respiratory support (Day) is defined as:

Date of first respiratory support – Date of Baseline Assessment + 1.

If the patient did not require respiratory support, the patient will be censored at the last known date the patient is known to not require respiratory support:

Final Date of Confirmation of no respiratory support needed - Date of Baseline Assessment + 1.

If a patient died before obtaining respirator support, the patient will be censored as a competing risk based on the following:

Date of Death - Date of Baseline Assessment + 1.

11.6.4 Time from first Oxygenation Support to first termination of Oxygenation Support:

This calculation is only applicable for those with oxygenation support.

The time to from first oxygenation support to first termination of oxygenation support is defined as:

Date of first termination of oxygenation support – Date of first oxygenation support + 1.

If the patient was still on oxygenation support, the patient will be censored at the last known date the patient is known to still on oxygenation support:

Final date of confirmation of still on oxygenation support - Date of first oxygenation support + 1.

If a patient died before terminating oxygenation support, the patient will be censored as a competing risk based on the following:

Date of Death - Date of Baseline Assessment + 1.

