2.3.2 Secondary endpoints

- Status on an ordinal scale assessed daily while hospitalized and on days 15 and 28 in IP versus control group patients
- NEWS assessed days 3, 5, 8, 11 while hospitalized and on days 15 and 29 in IP versus control group patients
- Rate of mechanical ventilation in IP versus control group patients
- Duration of mechanical ventilation (if applicable) in IP versus control group patients
- Duration of supplemental oxygen in IP versus control group patients
- Time to return to SpO₂ > 94% on room air
- Duration in ICU (if applicable) in IP versus control group patients
- Rate of Mortality in IP versus control group patients
- Duration of hospitalization in IP versus control group patients
- Time to discharge in IP versus control group patients
- Effect on the rate of change of partial pressure of oxygen (PaO₂) and PaO₂/FiO₂ ratio taken at baseline and measured once daily up to 2 weeks of treatment in IP versus control group patients

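### Ventilation duration is tabulated only in hour bins that merge 5 to 21 days into one row, with no continuous summary and a between-arm comparison only at 21 days

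*SAP*

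**What the plan says.** SAP 2.3.2 lists "Duration of mechanical ventilation (if applicable) in IP versus control group patients" as a secondary endpoint, as does Protocol 3.2. The analysis is in SAP 11.6.2, for each type of respiratory support: "Counts and percentages of patients with the following categories (based on total number of hours of respiratory support) will be reported".

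- **Hour rows.** Under 6, 6 to under 12, 12 to under 24, 24 to under 72, then from "72 hours but < 120 hours", then an open row above 120 hours.
- **Ongoing rows.** Support still running at data cut-off has its own rows, with the note "The hour can be amended based on real data".
- **Prolonged row.** The last row begins "Prolonged respiratory support (consecutive respiratory support for 21 days with at least" and goes on to require 6 or more hours per day.
- **Who is counted.** "The duration calculation is only applicable to patient with respiratory support".
- **Comparison of arms.** Newcombe 95% CIs and chi-squared p-values "will be computed between SOC and treatment arms A and B for prolonged respiratory support". Section 11.6.2 compares arms on nothing else.

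No other section covers how long ventilation lasts. SAP 11.6.1 is the proportion ever supported, 11.6.3 is time to starting support, and 11.6.4 is time to stopping oxygenation support only. Ventilator-free days to Day 29 is an objective in Protocol 3.1 and SAP 2.2.2, but no SAP section analyses it. Protocol 10.9.2 says that every secondary efficacy analysis will have a two-sided test at 5%.

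**The concern.** Four of the six hour bins describe the first three days of support. Everything from just over 5 days up to 21 days is one row. The same SAP's table of hospital and ICU stay (11.8.1) separates 7, 10, 14 and 21 days, so the coarse ventilation bins are not a general convention of the plan.

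Protocol 4.1 and SAP 2.1 say that Phase 2b data will be used to select and prioritise secondary endpoints for Phase 3. A table that cannot say whether ventilated patients typically needed one week or nearly three is a poor basis for that decision. It also leaves the next team without a median or a spread from which to plan. The test promised in Protocol 10.9.2 is supplied for this endpoint only at one cut, 21 days.

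**Working it through.** The plan states no power, sample size or expected value for ventilation duration, so there is no figure of its own to reproduce.

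**1. Durations mapped to rows (days × 24 h, continuous support)**

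| Duration | Hours | Row |
|---|---|---|
| 4 d | 96 | 72 to under 120 |
| 5 d | 120 | none |
| 6 d | 144 | above 120 |
| 14 d | 336 | above 120 |
| 20 d | 480 | above 120 |
| 21 d | 504 | above 120, and prolonged |

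Every completed continuous duration above 120 h and below 504 h lands in the same place. The hour rows use total hours and the prolonged row uses consecutive days, so intermittent support can fall elsewhere: 20 days × 5 h = 100 h is in the 72 to under 120 row.

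**2. Share of patients in the merged span.** Assume exponential ventilation times with median m days. Then P(>5 d) = 2^(−5/m) and P(5 to 21 d) = 2^(−5/m) − 2^(−21/m).

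| m (days) | P(>5 d) | P(>21 d) | P(5 to 21 d) |
|---|---|---|---|
| 5 | 0.50 | 0.05 | 0.45 |
| 7 | 0.61 | 0.125 | 0.48 |
| 10 | 0.71 | 0.23 | 0.47 |
| 14 | 0.78 | 0.35 | 0.43 |

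**3. Information lost in a comparison.** Simulated power, two-sided 5%, unadjusted, 2000 runs. Durations are log-normal with log-SD 0.8 and fully observed. The medians, the SD and the numbers ventilated are all assumptions. The rank test on the six hour bins is not in the SAP; it measures what the hour rows retain.

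| Medians (d) | Ventilated per arm | Rank test on hours | Rank test on hour bins | SAP 21-day chi-squared |
|---|---|---|---|---|
| 3 vs 6 | 15 | 58% | 53% | 1% |
| 6 vs 10 | 15 | 37% | 25% | 12.5% |
| 10 vs 20 | 15 | 59% | 19% | 44% |
| 3 vs 6 | 50 | 98% | 97% | 22.5% |
| 6 vs 10 | 50 | 87% | 70% | 48% |

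The hour rows hold up when durations are short and lose most when they are long. The planned 21-day test behaves the other way round. Neither recovers what the hours contain in the middle range.

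**4. The formula.** As printed, 11.6.2 defines duration as the end of support minus the end of support, which is 0 for everyone. Applied literally, every completed episode would be counted as under 6 hours.

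**5. How many patients.** Table 2 puts 1% of SOC patients in category 6 and 2% in category 5 at Day 15: 0.01 × 50 = 0.5 and 0.02 × 50 = 1. This is a one-day snapshot and not the number ever ventilated, but it suggests small counts. With 5 ventilated per arm, even the rank test on hours had only 9% to 27% power across the scenarios simulated.

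**The case against.** A reader might infer that this endpoint cannot show a difference at all, for instance that halving the median from 14 to 7 days would leave the table as it was. The documents do not support that. Under the exponential assumption above, that change moves the row above 120 h from 78% to 61%, the 24 to under 72 h row from 9% to 16%, the 72 to under 120 h row from 8% to 13%, and the share at 21 days or more from 35% to 12.5%. Under the log-normal assumption, medians of 6 and 10 days give 59% and 81% above 120 h, and 6% and 18% at 21 days. Nor is it right that no between-arm estimate is planned: the 21-day category has a CI and a p-value.

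Three further defences deserve weight.

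- SAP 11.1 calls the pilot phase essentially exploratory, SAP 11 plans patient listings for every efficacy endpoint, and SAP 11.4.2 analyses the ordinal scale, which includes ventilation status, through Day 29. These limit the loss but do not summarise duration.
- SAP 3.1 gives default statistics for continuous variables. It applies unless otherwise stated, and 11.6.2 states otherwise by specifying counts in categories. Sections that want the continuous summary, such as 10 and 11.7.1, invoke 3.1 by name.
- Few patients may be ventilated, so no method may find much. This stands, and it limits what the fix can deliver. It is also a reason not to discard information by binning.

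The permission to amend hours does not help, because it is attached to the ongoing rows and not to completed episodes.

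**Conclusion.** The point holds as one of table resolution and missing summary. For a stated secondary endpoint, the SAP gives no continuous summary of ventilation duration, merges completed continuous support between 5 and 21 days, leaves exactly 120 h unassigned, and compares arms only at 21 days. With exponential medians of 5 to 14 days, 43% to 48% of ventilated patients would lie in the merged span. That range and the power figures rest on assumed distributions and assumed numbers ventilated, while the bin layout and the gap at 120 h are facts of the text. Differences below 120 h, across 120 h and at 21 days remain visible. The change should be made, but it does not bear on the primary analysis.

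**What to change.** In SAP 11.6.2:

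1. Correct the formula to end minus start. Otherwise every new summary inherits a duration of zero.
2. Report duration as a continuous variable by arm (n, median, quartiles), separately for invasive and non-invasive ventilation, with the difference from SOC and a 95% CI.
3. Label that comparison descriptive. It is restricted to patients who were ventilated, a subset formed after randomisation.
4. State how deaths on support and support ongoing at cut-off are handled. Without a rule, an early death would count as a short duration.
5. Replace the open row with 120 h to under 7 d, 7 to under 10 d, 10 to under 14 d, 14 to under 21 d, and 21 d or more. This assigns 120 h and follows the cut-points of 11.8.1. It should not copy that table's edges, which overlap between 7 and 14 days and leave exactly 21 days unassigned.
6. Fix the cut-points of the ongoing rows now.

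The comparison over all randomised patients would be ventilator-free days to Day 29. Its missing analysis section is a separate gap that could be filled in the same revision.

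The cost is SAP wording and table shells, with no new data. The downside is sparse rows: with 50 patients per arm the finer bins may hold very few ventilated patients, so the median and quartiles should carry the message and the bins should be read as background.
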